### 1.3 Rationale for the Proposed Study

PD-1 inhibition is associated with dramatic and long lasting responses in melanoma. However, 40-60 % of patients do not respond to anti-PD-1 or anti-PD-L1 blocking antibodies. Recent reports of PD-1+CTLA4 blocking combinations have shown increased response rates. The combination of ipilimumab and nivolumab has demonstrated response rates in the ~60% range (19). The combination of low dose ipilimumab and standard dose pembrolizumab has been explored in a recent clinical trial and shown an ORR of 55%. However, there remains a residual 40% of patients where this combination is still not effective.

Our analysis has shown that many PD-1 non-responders share certain characteristics such as elevated LDH, liver metastasis, as well as increased tumor burden and non-cutaneous origin (21-23). Collectively, many of these melanoma patients have low fractions of partially exhausted cytotoxic T lymphocytes (peCTL). For these “low peCTL” tumors, ipilimumab + PD-1 combination therapy with ipilimumab and PD-1 inhibitors is the current standard of care. We hypothesize that the addition of aspirin to this modified ipilimumab pembrolizumab regimen will increase response rates.

Recent reports have highlighted other pathways that may be involved (20) such as iNOS, COX-2 activation, Myeloid Derived Suppressor Cells and Treg activation. A recent report provides powerful support for the COX-2 pathway as an escape mechanism(3). These authors showed that ablation of the COX-2 pathway or PGE synthetase in mice with the BRAFV600E mutation or the NRAS G12D mutation shifts cells towards the classic PD-1 escape pathway and hence sensitizes them to anti-PD-1 antibodies. The dose of aspirin was extrapolated from these mouse experiments.

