### 3.3.1 Inclusion Criteria

1. Patients must have histologically confirmed melanoma that is metastatic or unresectable and for which standard curative or palliative measures do not exist or are no longer effective
2. Age >18 years
3. Eastern Cooperative Oncology Group (ECOG) performance status of 0 to 1.
4. Requirements for organ and marrow function:

Adequate bone marrow function:

leukocytes	≥ 3,000/mcL
absolute neutrophil count	≥ 1,500/mcL
platelets	≥ 100,000/mcL

Adequate hepatic function:

total bilirubin	within normal institutional limits
total bilirubin	≤ 1.5 X institutional upper limit
AST(SGOT)	≤ 2.5 X institutional upper limit of normal
ALT(SGPT)	≤ 2.5 X institutional upper limit of normal

Adequate renal function:

creatinine	≤ 1.5 X ULN
------------	-------------

5. Women of childbearing potential should have a negative urine or serum pregnancy within 72 hours prior to receiving the first dose of study drug. If the urine test is positive or cannot be confirmed as negative, a serum pregnancy test will be required.
6. Women of childbearing potential (Section 5.6.2) must be willing to use an adequate method of contraception, as outlined in Section 5.6.2 – Contraception, for the course of the study through 120 days after the last dose of study medication.

Note: Abstinence is acceptable if this is the usual lifestyle and preferred contraception for the subject.

7. Men of childbearing potential (Section 5.6.2) must agree to use an adequate method of contraception as outlined in Section 5.6.2- Contraception, starting with the first dose of study therapy through 120 days after the last dose of study therapy.

Note: Abstinence is acceptable if this is the usual lifestyle and preferred contraception for the subject.

8. Ability to understand a written informed consent document, and the willingness to sign it.

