### 3.3.2 Exclusion Criteria

1. Any mental or physical condition or disease or past medical history that mitigates against following the protocol
2. History of active autoimmune diseases such as but not limited to Crohn's disease, Ulcerative colitis, Sjogren's syndrome, requiring active immune suppression. Patient may have hay fever or controlled asthma
3. Any solid organ transplant or bone marrow transplant
4. Any other disseminated malignancy. Exceptions include: localized prostate cancer, basal or squamous cell skin cancer, localized cervical cancer, and localized breast cancer.

5. Uncontrolled CNS metastasis. Patients with CNS metastasis can be eligible if definitively treated with radiotherapy or surgery.
6. Any coexistent medical condition interfering with drug absorption
7. History of gastritis or malabsorption syndrome or aspirin intolerance or allergy
8. Live vaccination within the last 30 days
9. History of multiple sclerosis, Type 1 DM or Guillain-Barre syndrome
10. Is pregnant or breastfeeding, or expecting to conceive or father children within the projected duration of the trial, starting with the screening visit through 120 days after the last dose of trial treatment.

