##### **6.1.5.2 Prior Treatment Details**

The investigator or qualified designee will review all prior cancer treatments including systemic treatments, radiation and surgeries.

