## 8 Statistical Analysis Plan

### 8.1 Statistical Analysis Plan Summary

This is a non-randomized prospective Phase II clinical trial with a Simon stage II design with an early stopping provision. The primary objective is to evaluate the overall response rate (ORR) by week 12 in patients with stage III unresectable/stage IV melanoma. The hypothesis is that the study treatment regimen will have a clinical meaningful improvement in ORR by week 12. H0 is for an ORR by week 12 = 60% while Ha is for an ORR by week 12= 80%. 60% is used as a threshold for the H0 based on published data (19).

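### The 60% null and 80% alternative are not tied to the patients whom inclusion criterion 1 admits, because prior PD-1/CTLA-4 therapy is left open

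*Combined protocol and SAP*

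**What the plan says.** **Eligibility.** Criterion 1 in Section 3.3.1 takes metastatic or unresectable melanoma "for which standard curative or palliative measures do not exist or are no longer effective". None of the eight inclusion or ten exclusion criteria mentions prior anti-PD-1, anti-PD-L1 or anti-CTLA-4 therapy. The nearest general exclusion is "Any mental or physical condition or disease or past medical history that mitigates against following the protocol", which concerns the ability to follow the protocol. Under Section 6.1.5.2 the investigator "will review all prior cancer treatments including systemic treatments, radiation and surgeries", but no limit is attached. Section 5.5.2 bars other immunotherapy only during screening and treatment.

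**Hypothesis.** Section 8.1 sets p0 = 60% and p1 = 80% for response by week 12. On the source it says "60% is used as a threshold for the H0 based on published data (19"). Section 1.3 cites the same reference for the response rate of ipilimumab plus nivolumab, about 60%. For low-dose ipilimumab plus pembrolizumab, the backbone used here, Section 1.3 gives 55%.

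**Status of the doublet.** Section 1.1 lists ipilimumab plus nivolumab among the standard treatments for advanced melanoma. Section 1.3 says of tumours with few partially exhausted cytotoxic T cells that "ipilimumab + PD-1 combination therapy with ipilimumab and PD-1 inhibitors is the current standard of care".

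**The concern.** A single-arm trial takes its control from outside, through p0. The comparison has meaning only if p0 is the rate the enrolled patients would have had without aspirin. Here the benchmark is the response rate of a regimen that the protocol counts as standard, while criterion 1 is worded for patients who have no standard option or in whom such options have stopped working. The absence of a prior-therapy rule allows patients already treated with one or both drug classes in the backbone.

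If such patients enter and respond less often, an active regimen may be abandoned after 11 patients or miss the final cutoff. The reported response rate would also reflect how many pretreated patients happened to be enrolled. Neither problem can be repaired by comparing the final figure with 60%.

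**Working it through.** **Step 1. Reproduce the plan's design.** Inputs: p0 = 0.60 and p1 = 0.80 (Section 8.1); 11 patients in stage 1, continuing if more than 7 respond (Sections 3.1 and 8.3); 43 in total (Section 8.2.1); final cutoff 30, so that 31 or more responses reject the null. With X1 ~ Bin(11, p) and X2 ~ Bin(32, p):

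- stage-1 stop: P(X1 ≤ 7)
- rejection: Σ over x = 8,…,11 of P(X1 = x) · P(X2 ≥ 31 − x)

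At p = 0.60, rejection is 0.0489 and the stage-1 stop is 0.704. At p = 0.80 they are 0.8024 and 0.161. These match the type I error and power in Section 8.4 and the 70% and 16% stopping probabilities in Section 8.2.1. The calculation is sound for the two rates it was given.

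**Step 2. Ask which population those rates belong to.** The 60% comes from a reference cited for the doublet's response rate. The documents do not state prior therapy for that reference. No passage gives a response rate for patients in whom standard therapy has stopped working, and none gives the expected share of pretreated patients. The mismatch is therefore textual and needs no assumption.

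**Step 3. Illustrate the sensitivity.** Assumptions: 80% response in checkpoint-naive patients, rate q in pretreated patients with q from 0.10 to 0.40, and a pretreated fraction f. The overall rate is p = 0.8(1 − f) + q·f. For f = 0.10 and q = 0.40, for example, p = 0.72 + 0.04 = 0.76.

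| Pretreated fraction f | Overall rate p (q = 0.10 to 0.40) | Power | Stage-1 stop |
|---|---|---|---|
| 0 | 0.80 | 0.80 | 0.16 |
| 10% | 0.73 to 0.76 | 0.49 to 0.64 | 0.34 to 0.26 |
| 20% | 0.66 to 0.72 | 0.18 to 0.44 | 0.55 to 0.37 |
| 30% | 0.59 to 0.68 | 0.04 to 0.26 | 0.73 to 0.49 |

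**Step 4. Direction under no aspirin effect.** Take 60% in naive patients, 10% pretreated, and q = 0.20 to 0.40. Then p = 0.54 + 0.02 = 0.56 up to 0.54 + 0.04 = 0.58, and rejection is 0.016 to 0.028, below 0.0489. The error runs towards missing an effect.

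**Step 5. Dependence on the stage-1 rule.** Section 8.2.1 gives a conflicting rule: continue with at least 4 responses. With the final cutoff unchanged, that rule makes the stage-1 stop about 1-3% at 30% pretreated, so the stopping figures in the table belong to the 7/11 rule. The loss of power does not depend on it. Under the rule of 4, power is 0.93 at p = 0.80 and 0.21 at p = 0.65 (30% pretreated, q = 0.30).

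**The case against.** The strongest reply is that criterion 1 is stock wording and that the team had patients not yet given the doublet in mind. Several passages fit this. The criterion has two branches, and treatment failure is only one of them. Section 1.1 calls ipilimumab plus nivolumab one of several standard treatments, and the standard-of-care sentence in Section 1.3 is limited to one tumour group. The hypothesis in Section 1.3 is that aspirin added to the regimen raises response, and Section 1.5 looks at patients not expected to respond to PD-1 monotherapy. A reader might infer that the trial admits only patients resistant to its own backbone; the documents do not support that. What stands is narrower: eligibility is applied as written, and as written it neither excludes pretreated patients nor fits the rationale.

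A second reply is that the size is assumed. That is correct. Fixing the pretreated rate at 10-40% also presupposes how the regimen performs in these patients, when overcoming PD-1 resistance is part of the trial's rationale. The ranges show sensitivity and do not estimate a loss.

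A third reply is that prior treatments are recorded and Section 8.4.1 allows supportive analyses by baseline characteristics. Those analyses are optional and do not change the primary test.

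**Conclusion.** The point holds: as written, p0 and p1 are not linked to the population that criterion 1 admits, and prior checkpoint therapy is uncontrolled. If pretreated patients respond less often, the consequence is lost power and a response rate that depends on case mix; a false claim for aspirin becomes less likely. The size rests on an assumed 80% rate in naive patients, an assumed 10-40% rate in pretreated patients, an assumed fraction, and the 7/11, 30/43 rule. On those terms even the mildest case shown, 10% pretreated responding at 40%, costs 0.80 − 0.64 = 0.16 of power.

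Two stronger conclusions are not supported. A reader might infer that the trial would stop for futility whatever aspirin does. Yet the stage-1 stop is 0.26-0.34 at 10% pretreated and 0.49-0.73 at 30%; a near-certain stop (0.97) needs an overall true rate as low as 40%. A reader might also infer that the 60% comes from checkpoint-naive patients, but the documents do not say so.

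**What to change.** Reconcile the standard-measures clause in criterion 1 with Sections 1.1 and 1.3 and with the hypothesis in Section 8.1, so that eligibility and p0/p1 describe the same patients. There are two ways.

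1. Define the 43-patient primary test population as patients with no prior anti-PD-1/PD-L1 or anti-CTLA-4 therapy. Report any pretreated patients separately, using the prior-treatment data already collected under Section 6.1.5.2. State why 60% suits that population, given the 55% cited for the backbone actually used.
2. Keep the wider population, state the permitted prior therapy, and justify p0 and p1 for it. Sample size need not change much. For assumed nulls of 20%, 30% and 40% with the 20-point gain, 5% one-sided level and 80% power kept, the optimal two-stage designs are 3/13, 12/43; 5/15, 18/46; and 7/16, 23/46. The total stays at 43 to 46, but the final cutoff falls from 30 to between 12 and 23.

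The first route costs an amendment to one criterion and its matching analysis text, and possibly slower accrual if pretreated patients were expected. The second costs a sourced benchmark and a recalculated decision rule.

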### 3.3.2 Exclusion Criteria

1. Any mental or physical condition or disease or past medical history that mitigates against following the protocol
2. History of active autoimmune diseases such as but not limited to Crohn's disease, Ulcerative colitis, Sjogren's syndrome, requiring active immune suppression. Patient may have hay fever or controlled asthma
3. Any solid organ transplant or bone marrow transplant
4. Any other disseminated malignancy. Exceptions include: localized prostate cancer, basal or squamous cell skin cancer, localized cervical cancer, and localized breast cancer.

5. Uncontrolled CNS metastasis. Patients with CNS metastasis can be eligible if definitively treated with radiotherapy or surgery.
6. Any coexistent medical condition interfering with drug absorption
7. History of gastritis or malabsorption syndrome or aspirin intolerance or allergy
8. Live vaccination within the last 30 days
9. History of multiple sclerosis, Type 1 DM or Guillain-Barre syndrome
10. Is pregnant or breastfeeding, or expecting to conceive or father children within the projected duration of the trial, starting with the screening visit through 120 days after the last dose of trial treatment.

### **3.4 Duration of Therapy**

In the absence of treatment delays due to adverse events, treatment may continue until:

- Disease progression
  - Note: For a clinically stable subject with first radiologic evidence of disease progression (e.g. unconfirmed), it is at the discretion of the primary investigator to continue treating the subject.
  - Note: A subject may be granted an exception, at the discretion of the primary investigator, to continue on treatment with confirmed radiographic progression if clinically stable or clinically improved.
- Inter-current illness that prevents further administration of treatment
- Unacceptable adverse event(s)
- Patients decides to withdraw from the study
- Significant patient non-compliance with protocol
- General or specific changes in the patients' condition render the patient unacceptable for further treatment in the judgment of the investigator.

### **3.5 Duration of Follow Up**

Patients will be followed for 30 days after completion of treatment or removal from study, or until death, whichever occurs first. Patients removed from study for unacceptable treatment related adverse event(s) will be followed until resolution or stabilization of all treatment related adverse events to Grade 2 or lower.

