### 2.2 Secondary

To determine the median progression free survival, overall survival, and toxicity profile of the combination of ipilimumab, pembrolizumab and high dose aspirin in patients with stage III unresectable/IV melanoma.

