#### **3.6.2 Study Completion**

The study will reach completion 36 months from the time the study opens to accrual.

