### 5.6.5 Subject Withdrawal/Discontinuation Criteria

Subjects may withdraw consent at any time for any reason or be dropped from the trial at the discretion of the investigator should any untoward effect occur. In addition, a subject may be withdrawn by the investigator or the Sponsor if enrollment into the trial is inappropriate, the trial plan is violated, or for administrative and/or other safety reasons. Specific details regarding discontinuation or withdrawal are provided in Section 6.3 - Other Procedures.

A subject must be discontinued from the trial for any of the following reasons:

- The subject or legal representative (such as a parent or legal guardian) withdraws consent.
- Confirmed radiographic disease progression

*Note:* For a clinically stable subject with first radiologic evidence of disease progression (e.g., unconfirmed), it is at the discretion of the site investigator to continue treating the subject

*Note:* A subject may be granted an exception to continue on treatment with confirmed radiographic progression if clinically stable or clinically improved.

- Unacceptable adverse experiences as described in Section 7.4
- Intercurrent illness that prevents further administration of treatment
- Investigator's decision to withdraw the subject
- The subject has a confirmed positive serum pregnancy test
- Noncompliance with trial treatment or procedure requirements
- The subject is lost to follow-up
- Administrative reasons

The End of Treatment and Follow-up visit procedures are listed in Section 6 (Protocol Flow Chart) and Section 6.3 - Other Procedures. After the end of treatment, each subject will be followed for 30 days for adverse event monitoring.

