##### **6.1.5.3 Subsequent Anti-Cancer Therapy Status**

The investigator or qualified designee will review all new anti-neoplastic therapy initiated after the last dose of trial treatment. If a subject initiates a new anti-cancer therapy within 30 days after the last dose of trial treatment, the 30 day Safety Follow-up visit must occur before the first dose of the new therapy. Once new anti-cancer therapy has been initiated the subject will move off-study.

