### **6.3.4 Follow-up Visits**

Patients who discontinue treatment will be followed as clinically indicated.

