### **9.6 Case Report Forms (CRFs)**

The Principal Investigator and/or his/her designee will prepare and maintain adequate and accurate participant case histories with observations and data pertinent to the study. Study specific Case Report Forms (CRFs) will document safety and treatment outcomes for safety monitoring and data analysis. All study data will be entered into OnCore® via standardized CRFs in accordance with the CTMS study calendar, using single data entry with a secure access account. The Clinical Research Coordinator (CRC) will complete the CRFs as soon as possible upon completion of the study visit; the Investigator will review and approve the completed CRFs.

The information collected on CRFs shall be identical to that appearing in original source documents. Source documents will be found in the patient's medical records maintained by UCSF personnel. All source documentation should be kept in separate research folders for each patient.

In accordance with federal regulations, the Investigator is responsible for the accuracy and authenticity of all clinical and laboratory data entered onto CRFs. The PI will approve all completed CRFs to attest that the information contained on the CRFs is true and accurate.

All source documentation and CTMS data will be available for review/monitoring by the UCSF DSMC and regulatory agencies.

The Principal Investigator will be responsible for ensuring the accurate capture of study data. At study completion, when the CRFs have been declared to be complete and accurate, the database will be locked. Any changes to the data entered into the CRFs after that time can only be made by joint written agreement among the Study Chair, the Trial Statistician, and the Protocol Project Manager.

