## Appendix 1 Schedule of Study Procedures and Assessments

Trial Period:	Screening Phase a	Treatment Cycles b								End of Treatment e	Post-Treatment Follow-up f
						To be repeated beyond 8 cycles					
Treatment Cycle/Title:	Main Study Screening	1	2	3	4	5	6	7	8	End of Treatment (EOT) visit	Safety Follow-up Visit
		-28 to -1	± 3	± 3	± 3	± 3	± 3	± 3	± 3		30 days post discon
Administrative Procedures											
Informed Consent	X										
Inclusion/Exclusion Criteria	X										
Demographics and Medical History	X										
Prior and Concomitant Medication Review	X										
Post-study anticancer therapy status										X	X
Survival Status										X	X
Trial Treatment Administration											
Ipilimumab		X	X	X	X						
Pembrolizumab		X	X	X	X	X	X	X	X		
Aspirin		X	X	X	X	X	X	X	X		
Clinical Procedures/Assessments											
Review Adverse Events		X	X	X	X	X	X	X	X		X
Full Physical Examination	X	X	X	X	X	X	X	X	X		X
Vital Signs and Weight	X	X	X	X	X	X	X	X	X		X
ECOG Performance Status	X	X	X	X	X	X	X	X	X		X
Laboratory Procedures/Assessments											
Pregnancy Test – Urine or Serum-HCG c	X										
PT/INR and aPTT	X										
CBC with Differential	X	X	X	X	X	X	X	X	X		
Comprehensive Serum Chemistry Panel	X	X	X	X	X	X	X	X	X		
Urinalysis	X										
T3, FT4 and TSH	X	X	X	X	X	X	X	X	X		
Tumor Tissue Collection g	X										
Efficacy Measurements											
Tumor Imaging d	X				X				X		

a. Screening procedures to be completed within 28 days of C1D1, except laboratory tests for screening should be performed within 10 days prior to the first dose of treatment.

- b. Patients will take aspirin daily and receive pembrolizumab and ipilimumab every 3 weeks for 4 cycles. After 4 cycles, ipilimumab will be discontinued and patients will continue receiving pembrolizumab every 3 weeks while taking aspirin daily.
- c. Women of childbearing potential: negative urine or serum pregnancy test within 72 hours prior to receiving trial treatment. If urine test is positive or non-confirmatory, a serum pregnancy test will be required.
- d. Prefer imaging of chest/abdomen and pelvis. PET/CT, CT, or MRI are acceptable.

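### Overall survival is to be reported as a Kaplan-Meier median, but no survival contact is scheduled beyond 30 days after treatment; a minor second point is an unresolved PFS rule for deaths before the first scan

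*Combined protocol and SAP*

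**What the plan says.** Section 2.2 sets the secondary objective: "To determine the median progression free survival, overall survival, and toxicity profile of the combination". Section 2.3.2 lists OS as an endpoint. Section 8.4.2 defines it from study day 1 to death from any cause, plans a Kaplan-Meier median with confidence intervals, and censors at the last date on which the patient is known to have been living.

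Follow-up is described in these places:

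- **Section 3.5** (the Abstract gives the same 30 days): "Patients will be followed for 30 days after completion of treatment or removal from study, or until death, whichever occurs first".
- **Section 6.1.5.3**: "Once new anti-cancer therapy has been initiated the subject will move off-study".
- **Section 6.3.4**: "Patients who discontinue treatment will be followed as clinically indicated", with no interval, duration or survival contact.
- **Appendix 1**: the row "Survival Status" is marked only at the end-of-treatment visit and the 30-day safety visit. Its footnotes allow the two to be combined.
- **Section 3.6.2**: "The study will reach completion 36 months from the time the study opens to accrual". Section 3.6.1 expects accrual to take 24 months.

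On PFS, section 8.4.2 counts death from any cause as an event. It also censors at day 1 any subject with no tumor assessment after baseline. Section 6.2.7 puts imaging at 12-week intervals.

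**The concern.** OS is measured to death, and many deaths can be expected after treatment ends. With 24 months of accrual and completion at month 36, each patient could be followed for 12 to 36 months. The schedule stops looking about one month after treatment.

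Two consequences follow. Few deaths are captured, so the planned median may not be reached. Censoring is also tied to the reason for stopping. If patients stop mainly for progression, those censored have a worse outlook than those still observed, and the curve reads too high. If they stop mainly for toxicity or complete response, it can read too low.

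The PFS issue is smaller. A death before the first scan at about week 12 satisfies both rules in 8.4.2, and neither is given precedence.

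**Working it through.** **1. Figures in the plan.** No OS or PFS event count, rate or precision is stated, so there is no survival figure to reproduce. The one relevant design figure is the 70% probability of stopping at stage 1 if the response rate is 60% (section 8.2.1). It reproduces under the rule of stopping at 7 or fewer responses in 11 (sections 3.1 and 8.3): P(X ≤ 7 | n = 11, p = 0.6) = 0.704. Everything below assumes that the trial continues to 43 patients.

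**2. One scenario by hand (all rates assumed).** Times are exponential. Median time to a progression stop is 4 months, median survival afterwards is 6 months, and the on-treatment death hazard is d = 0.01 per month. Then λp = ln 2/4 = 0.1733, λs = ln 2/6 = 0.1155 and L = λp + d = 0.1833.

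- True 12-month OS: e^(−12L) + λp[e^(−12λs) − e^(−12L)]/(L − λs) = 0.1109 + 0.1733 × (0.2500 − 0.1109)/0.0678 = 0.47.
- OS as read when censored one month after stopping: after month 1, each patient on treatment is matched by r = λp[e^(L − λs) − 1]/(L − λs) = 0.179 living patients inside the 30-day window. The observed hazard is (d + λs·r)/(1 + r) = (0.0100 + 0.0207)/1.179 = 0.0260 per month. The cumulative hazard to month 12 is 0.018 (first month) + 11 × 0.0260 = 0.305, and e^(−0.305) = 0.74.
- Observed at risk at 12 months: 43 × 0.1109 × 1.179 = 5.6, against 43 × 0.467 = 20.1 with full follow-up.

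**3. Examples by simulation.** Entry is uniform over 24 months with cutoff at month 36. Each cell reads no later tracing / full follow-up.

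| Scenario | 12-month OS | Deaths of 43 | Median reached |
|---|---|---|---|
| Progression 4, then survival 6 | 0.74 / 0.47 | 6.6 / 35.4 | 31% / 100% |
| Progression 9, then survival 18 | 0.87 / 0.79 | 5.4 / 18.7 | 14% / 79% |
| Reversal case | 0.71 / 0.77 | 6.2 / 17.1 | 31% / 53% |

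The reversal case has mostly toxicity or complete-response stopping (median 4 months; progression 12). Survival afterwards is 48 months, or 12 after progression. In it, 70% of progressors are treated 6 months past progression and d = 0.02.

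**4. Grid of 120 assumed scenarios, d = 0.01.** Medians in months: progression stop 4, 6, 9 or 12; other stop none, 6 or 12; survival after progression 6, 12 or 18; survival after another stop 24 or 48; 0 or 30% treated 3 months past progression.

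- No later tracing: 3-10 deaths captured instead of 15-35; 2-21 at risk at 12 months instead of 20-35; median reached in 9-53% of trials instead of 39-100%; 12-month OS 4-27 points too high.
- Full status from records for a random half: 9-22 deaths; 1-8 points too high; median reached in 36-100%.
- Half of later deaths found, but survivors left censored at the 30-day visit: from 14 points too low to 6 too high, and too low in 99 of 120 scenarios.

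With no on-treatment death hazard, six simpler scenarios (progression median 6 or 12, survival afterwards 6, 12 or 18) capture about 1-4 deaths instead of 13-32.

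**5. PFS, if the day-1 rule prevails.** Let q be the share of patients who die on treatment before day 84. Censoring them at day 1 makes the reported median solve S(t) = 0.5(1 − q), so with exponential PFS t = m[1 − log2(1 − q)] for a true median m. For q = 1.8-2.6% (43q = 0.8-1.1 patients), a true 6 months reads 6.16-6.23 and a true 9 reads 9.24-9.34. If every death before day 84 lacked a scan (q = 3.3-8.2%), these become 6.29-6.74 and 9.44-10.11.

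**The case against.** - **Later deaths can count.** This is true. Section 8.4.2 censors by last known date, and section 9.6 places source documents in the "medical records maintained by UCSF personnel". But nothing schedules that search or requires it equally for living patients. Tracing deaths alone tends to push the estimate too low.
- **Section 5.6.5 as a limit on survival follow-up.** A reader might cite "After the end of treatment, each subject will be followed for 30 days for adverse event monitoring". That sentence concerns adverse events only. The case rests on the Abstract, 3.5, 6.1.5.3 and Appendix 1.
- **The inputs are assumed, and the top of the range is strained.** This stands. The 27-point error needs a 4-month progression median, 6 months' survival afterwards and no other reason for stopping. That median leaves only about 62% progression-free at week 12 (2^(−2.76/4)), barely compatible with the 60% null response rate and not with the 80% alternative. Sections 3.4 and 5.6.6 also allow stopping for toxicity or complete response.
- **The trial may stop at 11 patients.** This stands. OS would then be barely informative under any follow-up. The calculations also leave out the interim pause and the possible enrolment of up to 50.
- **Consequence.** OS and PFS are secondary and untested, and full follow-up would not guarantee a median: it is reached in only 39% of trials in the least favourable grid scenario. This limits the weight of the point but does not remove the gap.

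**Conclusion.** The gap is established by reading alone: OS has a planned Kaplan-Meier median, and no survival contact is scheduled after the 30-day visit. As written, most deaths after treatment would be missed unless found incidentally, censoring at the end of treatment is probably informative, and the median would often not be reached. The direction of the error depends on why patients stop and on how they are traced. The figures of 3-10 deaths instead of 15-35, and of a 4-27 point overstatement, illustrate the case of no later tracing in 43 patients under assumed rates. They are not predictions.

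A reader might infer that no OS figure from this trial could be relied on, or that OS must be overstated. The documents support neither. In the milder scenarios the 12-month error is a few points, with half the patients traced it is 1-8 points, and the reversal case reads about 5 points too low. The response-rate decision is untouched.

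The PFS conflict is real but minor: about 1 patient of 43 and 0.2-0.3 months on the median. The 6-month PFS proportion is unaffected, because 8.4.2 already counts unassessed subjects as failures.

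**What to change.** **(a) Survival follow-up.** Amend the Abstract, 3.5, 6.1.5.3, 6.3.4 and Appendix 1 together. Collect survival status by phone or records at a regular interval after end of treatment, for example every 12 weeks, until death, withdrawal of consent or the 36-month study completion, whether or not new therapy has started. Record a last-known-alive date for living patients as well as dates of death. Keep the 30-day limit for adverse event follow-up.

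**(b) PFS rule.** In 8.4.2, state that a death with no scan after baseline is a PFS event on the date of death. Censor at day 1 only subjects with no scan who are not known to have died. Leave the 6-month proportion as it is, and settle the wording before the data are known.

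**Cost.** One amendment with PRC and IRB approval (section 9.4), and possibly revised consent wording for contact after a patient has left the study. Staff time is about 2-5 checks per patient, or roughly 100-220 for 43 patients. No clinic visits or scans are added. Part (b) is a one-sentence change.
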